## PROTOCOL SYNOPSIS

**Title:** Phase I Trial of Cabozantinib (XL184) for Advanced Solid Tumors in Persons with HIV Infection

**Phase of Study:** Phase I

**Participating Institutions:** This protocol will be open to all AMC member sites.

**Accrual Target:** 16 to 42 participants

**Population:** Participants with incurable recurrent or metastatic solid tumors and HIV infection.

**Regimen:** This is a phase I, dose escalation study of cabozantinib (XL184) for advanced solid tumors in persons with HIV infection. Cabozantinib will be administered orally as a once daily dose continuously for 28-day cycles, according to the Protocol Schema. Participants will be stratified into three groups based on which HAART therapy they are receiving. The first group (**Stratum A**) will be participants on either ritonavir or cobicistat (potent CYP3A4 inhibitor)-containing antiretroviral therapy. Since a potential interaction leading to higher drug levels of cabozantinib in participants on ritonavir or cobicistat is expected, participants will be dose escalated, starting at ~33% of the standard dose (60 mg), using a classic 3 + 3 phase I clinical trial design. Dose increases will be in 20 mg increments to a maximum of 60 mg/day. The second group (**Stratum B**) will be participants being treated with either efavirenz or etravirine-containing regimens, in whom CYP3A4 induction may lead to lower levels of the study drug. These participants will be treated at the standard dose of cabozantinib, then dose escalated by 20 mg/cohort to a maximum of 100 mg/day in a 3 + 3 design. The third group (**Stratum C**) will include participants taking antiretrovirals not specified in Stratum A or B, or who are not receiving active antiretroviral therapy. These participants will be treated at the standard dose of 60 mg/day; no dose escalation is planned in this Stratum.

In this trial, a dose-limiting toxicity (DLT) will be defined as any cabozantinib-related grade 3 or 4 non-hematologic toxicity during the first cycle of therapy, including grade 3 nausea and/or vomiting and grade 3 diarrhea despite prophylaxis and/or treatment or any of the following grade 4 hematologic toxicities during the first cycle of therapy: thrombocytopenia, neutropenia of more than 5 days duration, and neutropenia of any duration with fever or documented infection; additionally, treatment delay of 14 days or greater during Cycle 1 due to unresolved toxicity or any

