#### Adverse events

The clinical studies with cabozantinib are ongoing and thus the AE data from the clinical database as of March 1, 2011 and May 4, 2011 do not yet include all SAEs (Exelixis Communication, 2011). As of March 2011, AE data are available for 913 subjects who have been dosed with cabozantinib (806 in single-agent studies and 107 in combination studies of cabozantinib with erlotinib, rosiglitazone, or TMZ  $\pm$  radiation) (Investigator's Brochure, 2012). Data from the 806 subjects who received single-agent cabozantinib show that the most frequently ( $>20\%$ ) observed AEs regardless of causality were fatigue, diarrhea, nausea, decreased appetite, constipation, palmar-plantar erythrodysesthesia (PPE) syndrome, vomiting, dysphonia, and hypertension. Effects that may be related to the inhibition of VEGF, including hypertension, thromboembolic events, GI perforation, fistula formation, hemorrhage, wound dehiscence, and proteinuria, have been observed in the single-agent and combination cabozantinib studies. The most commonly reported SAEs that were assessed as related to study treatment with cabozantinib (as a single-agent or combination) were pulmonary embolism (PE), diarrhea, dehydration, deep vein thrombosis (DVT), vomiting, nausea, thrombocytopenia, fatigue, wound dehiscence, and PPE syndrome.

There have been 15 grade 5 AEs related to study treatment: GI hemorrhage (two subjects), PE (two subjects), respiratory failure (two subjects), respiratory disorder (one subject), hemoptysis (one subject), death due to unknown cause (two subjects), intracranial hemorrhage (one subject), intestinal perforation (one subject), enterocutaneous fistula (one subject), hemorrhage (presumed to be hemoptysis; one subject), and diverticular perforation, peritonitis (one subject) (Investigator's Brochure, 2012).

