## 5.0 TREATMENT PLAN

### 5.1 Agent Administration

Treatment will be administered on an outpatient basis. Reported adverse events and potential risks are described in [Section 7.0](#). Appropriate dose modifications are described in [Section 6.0](#). No investigational or commercial agents or therapies other than those described below may be administered with the intent to treat the participant's malignancy.

Cabozantinib will be administered orally as once daily doses continuously over 28 day cycles in each of three treatment strata in participant cohorts as detailed in the table below. The starting dose in each treatment Stratum will be Dose Level 1. Dose escalation will proceed in participant cohorts within each Stratum according to the scheme described in [Section 5.2](#).

**NOTES: The participant will be requested to maintain a medication diary of each dose of medication. The medication diary will be returned to clinic staff at the end of each course.**

**The site will be required to document study agent return by participant in source documents. Non-compliance with study agent administration should be noted at the time of diary collection and the participant should be instructed again regarding dosing instructions.**

**Missed cabozantinib doses will NOT be made up. Participants who have missed a dose should wait until the next scheduled dose to resume therapy.**

For Stratum A, one dose de-escalation cohort (Dose Level -1) will be permitted for excessive toxicity observed at the initial (Dose Level 1) cohort. For Stratum B and Stratum C, two dose de-escalation cohorts (up to Dose Level -2) will be permitted for toxicity observed at initial cohorts.

For participants treated on Stratum A no dose escalation will proceed beyond Dose Level 3 (60 mg). For participants treated on Stratum B, no dose escalation will proceed beyond Dose Level 2 (100 mg). For participants treated on Stratum C, no dose escalation will proceed beyond Dose Level 1.

Dose Escalation Schedule			
Dose Level	Dose of Cabozantinib (XL184)*		
	Stratum A ART Regimens Including Drugs that Inhibit CYP3A4 A (mg/day)	Stratum B ART Regimens Including Drugs that Induce CYP3A4 B (mg/day)	Stratum C All Other ART Regimens C (mg/day)
Level -2	-	20	20
Level -1	20 mg every other day	40	40
Level 1	20	60	60
Level 2	40	100	-
Level 3	60	-	-

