### 5.2 Definition of Dose-Limiting Toxicity

Dose escalation decisions for cabozantinib will be made after evaluation of toxicities in the first cycle of therapy. In this trial, a dose-limiting toxicity (DLT) will be defined as any cabozantinib-related grade 3 or 4 non-hematologic toxicity during the first cycle of therapy, including grade 3 nausea and/or vomiting and grade 3 diarrhea despite prophylaxis and/or treatment or any of the following grade 4 hematologic toxicities during the first cycle of therapy: thrombocytopenia and neutropenia of any duration (with or without fever or documented infection); additionally, treatment delay of greater than 7 days during Cycle 1 due to unresolved toxicity or any dose reduction required during Cycle 1 due to a cabozantinib-related adverse event (including for intolerable cabozantinib-related grade 2 non-hematological toxicity – per Table 6-1) will be considered a DLT.

For all participants who experience a DLT or other persistent and severe toxicity, a blood sample for pharmacokinetics analysis will be requested from the participant (if feasible). The samples should be drawn as close as possible to the time of the event.

If a DLT occurs in one participant at a particular dose level, up to 3 additional participants will be added to that cohort. If a second participant experiences a DLT, the maximally tolerated dose (MTD) of the study will have been exceeded. If 2 DLTs are experienced at the first cohort, one dose level de-escalation (Dose Level -1) will be permitted according to the study schema suggested in the treatment plan.

Management and dose modifications associated with the above adverse events are outlined in [Section 6.0](#).

Dose escalation will proceed in participant cohorts within each Stratum ([Section 5.1](#)) according to the following scheme. Participants are considered evaluable for the purpose of cohort dose escalations if in the first cycle they either experience a DLT (defined above), or receive at least 80% of the planned treatment dose and are followed for one full cycle without a DLT. Participants receiving less than 80% of the treatment dose during cycle 1 without a DLT may be replaced for the purpose of safety and PK evaluation at the discretion of the study team.

Number of Participants with DLT at a Given Dose Level	Escalation Decision Rule
0 out of 3	Enter 3 participants at the next dose level.

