#### **5.4 Duration of Therapy**

In the absence of treatment delays due to adverse event(s), treatment may continue until one of the following criteria applies:

- Disease progression,
- Intercurrent illness that prevents further administration of treatment,
- Dose-limiting toxicity (DLT requiring discontinuation of therapy, as defined in [Section 5.2](#)). Dose reductions in the first cycle of therapy for cabozantinib-related adverse events are permitted.
- Other unacceptable adverse event(s),
- Treatment delay of 14 days or greater during Cycle 1 due to unresolved toxicity (DLT definition, [Section 5.2](#)).
- Treatment delay in subsequent cycles > 6 weeks due to toxicity (treatment delays for other reasons may be permitted at the discretion of the Study Chairs),
- Participant decides to withdraw from the study.
- General or specific changes in the participant's condition render the participant unacceptable for further treatment in the judgment of the investigator, including:
  - Necessity for treatment with other anticancer treatment prohibited by the protocol.
  - Change to a ritonavir or cobicistat-containing antiretroviral regimen for a participant enrolled on a different study arm (see [Section 5.3.1.2](#)).
  - Sexually active participants who refuse to use medically accepted barrier methods of contraception (e.g., male condom, female condom) during the course of the study and for 6 months following discontinuation of study treatment.
  - Women who become pregnant or are breastfeeding.
- Request by regulatory agencies for termination of treatment of an individual participant or all participants under the protocol.
- Significant noncompliance with the protocol schedule in the opinion of the investigator.
- The minimum dose of study treatment for Stratum A will be the Dose Level -1 dose, and the lowest dose of study treatment for Stratum B and Stratum C will be the Dose Level -2 dose. Participants who cannot tolerate the lowest Dose Level dose for the specified study Stratum will have study treatment discontinued.

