## 12.0 STATISTICAL CONSIDERATIONS

### 12.1 Study Design/Endpoints

This is a phase I, dose escalation study of cabozantinib for advanced solid tumors in persons with HIV infection. The primary endpoint of the study is the safety and tolerability of single agent cabozantinib and to determine the maximal tolerated dose (MTD) in this participant population. The study will be a standard phase I dose escalation trial with a 3+3 design. The study agent will be administered continuously in 28 day cycles.

Participants will be stratified based on HAART with the currently recommended dosing regimen. Participants on ritonavir or cobicistat (potent CYP3A4 inhibitor)-containing HAART will be on Stratum A; participants on efavirenz or etravirine (CYP3A4 inducer)-containing HAART will be on Stratum B, and all other participants (including those without antiretroviral therapy) will be on Stratum C. Dose escalation and MTD determination will be done for each stratum individually. Participants are considered evaluable for the purpose of cohort dose escalations if in the first cycle they either experience a dose-limiting toxicity (DLT) (see below), or receive at least 80% of the planned treatment dose and are followed for one full cycle without a DLT. Participants receiving less than 80% of the treatment dose during cycle 1 without a DLT may be replaced for the purpose of safety and PK evaluation at the discretion of the study team.

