Dose escalation decisions for cabozantinib will be made after evaluation of toxicities in the first cycle of therapy. In this trial, a dose-limiting toxicity (DLT) will be defined as any cabozantinib-related grade 3 or 4 non-hematologic toxicity during the first cycle of therapy, including grade 3 nausea and/or vomiting and grade 3 diarrhea despite prophylaxis and/or treatment or any of the following grade 4 hematologic toxicities during the first cycle of therapy: thrombocytopenia and neutropenia of any duration (with or without fever or documented infection); additionally, treatment delay of greater than 7 days during Cycle 1 due to unresolved toxicity or any dose reduction required during Cycle 1 due to a cabozantinib-related adverse event will be considered a DLT. If a DLT occurs in one participant at a particular dose level, up to 3 additional participants will be added to that cohort. If a second participant experiences a DLT, the maximally tolerated dose (MTD) of the study will have been exceeded. If 2 DLTs are experienced at the first cohort, dose de-escalation cohorts (up to Dose Level -1 for Stratum A; up to Dose Level -2 in Stratum B and Stratum C) will be permitted according to the study schema suggested in the treatment plan.

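### The Cycle 1 DLT definition differs between the Synopsis and Sections 5.2, 5.4 and 12.1 on treatment delay and grade 4 neutropenia, and no version says how a related death is counted

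*Combined protocol and SAP*

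**What the plan says.** The DLT definition appears in the Protocol Synopsis, Section 5.2 and Section 12.1. All three share a core, in Section 5.2: "a dose-limiting toxicity (DLT) will be defined as any cabozantinib-related grade 3 or 4 non-hematologic toxicity during the first cycle of therapy". Each adds listed grade 4 hematologic toxicities, a Cycle 1 delay for unresolved toxicity, and a Cycle 1 dose reduction for a related event. They differ or are silent as follows.

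- **Delay.** Section 12.1 has "treatment delay of greater than 7 days during Cycle 1 due to unresolved toxicity", and Section 5.2 agrees. The Synopsis has "treatment delay of 14 days or greater during Cycle 1 due to unresolved toxicity". Section 5.4, in its list of reasons to end treatment, has "Treatment delay of 14 days or greater during Cycle 1 due to unresolved toxicity" and tags this in parentheses as the DLT definition of Section 5.2. Section 6.0 also uses 14 days, but only as a discontinuation rule.
- **Grade 4 neutropenia.** It is a DLT at any duration in Sections 5.2 and 12.1. In the Synopsis it must last more than 5 days or come with fever or documented infection.
- **Grade 5.** No version names it. The expedited-reporting table in Section 7.3.3 does cover grades 3 to 5.
- **Evaluability.** Without a DLT, participants count for escalation only if they "receive at least 80% of the planned treatment dose and are followed for one full cycle without a DLT" (Section 12.1; Section 5.2 agrees). Those below 80% without a DLT "may be replaced for the purpose of safety and PK evaluation at the discretion of the study team" (Section 5.2).

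**The concern.** The number of Cycle 1 DLTs in a cohort is the only input to the decision table in Section 5.2, and the MTD is part of the primary endpoint. With cohorts of three to six, one participant's classification can decide the outcome: 0 of 3 (next level) becomes 1 of 3 (enter at least three more), or 1 of 6 (proceed) becomes 2 of 6 (stop). If the classification depends on which section is read, or on a replacement choice made once the toxicity is known, the written rule does not fix the result.

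**Working it through.** **Background figure.** Expected enrolment in Section 12.2 reproduces from the stratum ranges: 4 + 6 + 6 = 16 and 18 + 18 + 6 = 42. Nothing below depends on it.

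**1. Dose fractions.** Inputs: 28-day cycles with continuous daily dosing (Section 12.1), missed doses not made up (Section 5.1), 80% threshold (Sections 5.2 and 12.1). 0.8 × 28 = 22.4, so 23 doses are needed and at most 5 may be missed. Assume one hold, no other missed dose, an event that meets no other DLT criterion, and restart at the same dose.

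| Days held | Doses taken | Share | More than 7 days (5.2, 12.1) | 14 days or more (Synopsis, 5.4 label) |
|---|---|---|---|---|
| 5 | 23/28 | 82.1% | not a DLT, evaluable | not a DLT, evaluable |
| 6 | 22/28 | 78.6% | not a DLT, replaceable | not a DLT, replaceable |
| 7 | 21/28 | 75.0% | not a DLT, replaceable | not a DLT, replaceable |
| 8 | 20/28 | 71.4% | DLT | not a DLT, replaceable |
| 13 | 15/28 | 53.6% | DLT | not a DLT, replaceable |
| 14 | 14/28 | 50.0% | DLT | DLT |

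Holds of 8 to 13 days are classified in opposite ways. Holds of 6 or 7 days (6 to 13 under the 14-day wording) are neither DLTs nor evaluable. The main case is a first intolerable grade 2 event, for which Table 6-1 leaves the restart dose to the investigator. The same event managed by dose reduction is a DLT.

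**2. Neutropenia.** Take grade 4 neutropenia lasting 5 days or less, without fever or infection. It is a DLT under Sections 5.2 and 12.1, but not under the Synopsis neutropenia clause. One limit applies: Table 6-2 has treatment resume at a reduced level after grade 4 neutropenia. If that reduction falls within Cycle 1, the Synopsis dose-reduction clause would normally make it a DLT as well. The conflict therefore matters mainly when no reduced restart occurs in Cycle 1.

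**3. Related death in Cycle 1 that meets no other criterion.** Read literally, it is not a DLT. The participant is also not evaluable, because one full cycle was not completed. After 22 or fewer doses (at most 78.6%) the replacement sentence applies. After 23 to 27 doses (82.1% to 96.4%) it does not, and no status is given. The decision table omits the death in both cases.

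**4. What one such classification does.** Under the Section 5.2 table, with DLT probability p in each other participant:

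- Replaced: P(escalate) = (1−p)³ + 3p(1−p)⁵.
- Counted, event among the first three: the other two and the next three must all be free of DLT, so (1−p)² × (1−p)³ = (1−p)⁵.

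| Assumed p | Replaced | Counted |
|---|---|---|
| 0.10 | 0.729 + 0.177 = 0.91 | 0.59 |
| 0.20 | 0.512 + 0.197 = 0.71 | 0.33 |
| 0.30 | 0.343 + 0.151 = 0.49 | 0.17 |

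The same pairs hold for an 8-to-13-day hold that is counted under one wording and replaced under the other. They apply only where Section 5.1 allows escalation: Stratum A Levels 1 and 2, and Stratum B Level 1.

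**The case against.** **The delay conflict is editorial.** The two full statements in the body, Sections 5.2 and 12.1, agree. A 14-day stopping rule can coexist with a 7-day DLT rule, so Section 6.0 is no contradiction. This stands as far as it goes, and a reader who counts every 14-day passage as a conflict would overstate the case. But the Synopsis gives 14 days within its own DLT definition, and Section 5.4 attributes 14 days to Section 5.2, which says otherwise. Those two places do conflict with Sections 5.2 and 12.1.

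**Nobody would ignore a related death.** A reader might infer that the plan lets treatment-related deaths vanish. The documents do not support that. Any related grade 3 or 4 non-hematologic event recorded before the death is already a DLT. Replacement is discretionary. Section 11.1.1 keeps every treated participant evaluable for toxicity. Appendix V has the Protocol Chair, Medical Monitor and Group Statistician judge whether the escalation criteria are met, and they would probably count the death. What remains is that Appendix V bases escalation on the protocol's rules, and those rules do not require counting it.

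**The prior deaths prove little.** Section 2.4 says "There have been 15 grade 5 AEs related to study treatment". Of these, 13 have a named cause and two are of unknown cause. The text does not give them by cycle, tie them to a denominator, or show that any would have escaped this definition. They make grade 5 worth naming, but they yield no Cycle 1 rate. This objection stands in full.

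**The 80% gap is narrow.** Also correct. Related grade 3 or 4 non-hematologic events and restarts at a reduced dose are already DLTs, and the note to Table 6-1 limits Cycle 1 holds for lower-grade toxicity.

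**Conclusion.** The point holds, with parts of unequal weight. The main defect is that the DLT definition is not the same throughout: holds of 8 to 13 days (71.4% down to 53.6% of doses) get opposite statuses, and grade 4 neutropenia is defined more narrowly in the Synopsis. Both follow directly from the text. The missing grade 5 is secondary, since it needs a death with no earlier qualifying event and a literal reading of the rule. The gap for short holds is minor.

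The contrast of 0.71 with 0.33 should not be read as the size of a bias in this trial. It is the effect of one DLT in any 3+3 design at an assumed 20% rate (0.91 and 0.59 at 10%; 0.49 and 0.17 at 30%), given that the event occurs. Nor do the documents show that the short-hold gap pushes the MTD up: neither the direction nor the size of its effect can be established.

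**What to change.** - Reconcile the delay criterion across the Synopsis and Sections 5.2, 5.4 and 12.1, including the label in Section 5.4, and the grade 4 neutropenia criterion across the Synopsis and Sections 5.2 and 12.1. The thresholds are the sponsor's choice. A separate discontinuation threshold may remain if it is not called the DLT definition.
- State in the Synopsis and Sections 5.2 and 12.1 that cabozantinib-related grade 5 events in Cycle 1 enter the escalation count and that these participants are not replaced.
- Fix in advance the escalation status of participants who fall below 80% of the planned dose because of related toxicity. Whether such shortfalls count as dose-limiting is for the sponsor to decide.

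The cost is an amendment to wording in four places. If a related death that meets no other criterion occurs, escalation becomes more conservative, as the second table shows. The effect of the other two changes depends on the sponsor's choices and cannot be sized from the documents.

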**Duration:**

Treatment may continue indefinitely until one of the following criteria applies: 1) unacceptable toxicity (including DLT in cycle 1); 2) progressive disease; or 3) participant withdrawal or removal.

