#### **5.5 Duration of Follow Up**

Participants will be followed for 30 days after removal from study or until death, whichever occurs first. Participants removed from study for unacceptable adverse event(s) will be followed until resolution or stabilization of the adverse event.

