## 6.0 DOSING DELAYS/DOSE MODIFICATIONS

### Dose modifications for Cabozantinib (XL184)

Toxicities warranting treatment delays and dose modifications, along with supportive care guidelines, are noted below.

Stratum-based dose de-escalation of cabozantinib will be permitted for participants experiencing specified toxicity when treated at a particular dose level, as noted below; reductions will be at one-dose-level increments. In no case will dose de-escalation occur beyond the lowest specified Dose Level dose for a particular Stratum (Dose Level -1 for Stratum A; Dose Level -2 for Stratum B and Stratum C). Dose reductions are permanent. No intra-participant dose escalation will be permitted.

**NOTE: Dose modification during Cycle 1 WILL be permitted.** Participants will be permitted to continue study therapy provided no other criteria for protocol discontinuation apply ([Section 5.4](#)). **HOWEVER, treatment delay of 14 days or longer due to unresolved toxicity during Cycle 1 will require discontinuation of study treatment** ([Section 5.4](#)).

**NOTE:** If a participant experiences several adverse events and there are conflicting recommendations, the investigator should use the recommended dose adjustment that reduces the dose to the lowest level.

**NOTE:** Starting in Cycle 2, if toxicity requiring treatment delay does not resolve in less than or equal to 6 weeks, the study treatment will be discontinued. Treatment delays for other reasons may be permitted at the discretion of the Study Chairs.

Dose De-Escalation Schedule			
Dose Level	Dose of Cabozantinib (XL184)*		
	Stratum A ART Regimens Including Drugs that Inhibit CYP3A4 A (mg/day)	Stratum B ART Regimens Including Drugs that Induce CYP3A4 B (mg/day)	Stratum C All Other ART Regimens C (mg/day)
Level -2	-	20	20
Level -1	20 mg every other day	40	40
Level 1	20	60	60
Level 2	40	100	-
Level 3	60	-	-

\* Cabozantinib (XL184) must be taken whole and on an empty stomach. Participants must fast for 2 hours before and 1 hour following each dose of cabozantinib (XL184). To permit pharmacokinetic sampling studies, AM dosing is required during the first cycle of therapy.

AStratum A: Participants taking either ritonavir-boosted or cobicistat-boosted ART regimens

BStratum B: Participants taking either efavirenz or etravirine-based ART regimens.

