<math>\geq</math> 1.5 fold increase of AST or ALT AND both AST and ALT are <math>\leq</math> 5.0 x ULN	
Continue cabozantinib treatment with at least twice weekly monitoring of LFTs for 4 weeks and weekly for 4 weeks. If LFTs continue to rise, interrupt study treatment. Then continue with at least weekly LFTs until resolution to Grade <math>\leq</math> 1. Study treatment may then be resumed at a one-dose-level reduction of cabozantinib.

<math>\geq</math> 1.5 fold increase of AST or ALT and at least one of AST or ALT is Grade 3 (i.e. AST or ALT <math>></math> 5.0 but <math>\leq</math> 20.0 x ULN)	
Interrupt study treatment and monitor with at least twice weekly LFTs until Grade <math>\leq</math> 2. Then continue with at least weekly LFTs until resolution to Grade <math>\leq</math> 1. Study treatment may then be resumed at a one-dose-level reduction of cabozantinib.

Grade 4	
Discontinue study treatment permanently. LFTs should be monitored as clinically indicated, at least 2-3 times per week, until resolution to Grade <math>\leq</math> 1. If the subject was unequivocally deriving

	clinical benefit, the subject may be able to resume treatment at a lower dose as determined with Study Chair approval.
--	--

Cabozantinib treatment should also be interrupted when transaminase increases are accompanied by progressive elevations of total bilirubin, and/or elevations of coagulation tests (e.g., International Normalized Ratio [INR]). Monitoring of transaminases should be intensified (2–3 times per week) and cabozantinib should be held until the etiology of the abnormalities is determined and these abnormalities are corrected or stabilize at clinically acceptable levels (INR < 1.5 × ULN, total bilirubin < 1.5 × ULN, aminotransferases ≤ baseline grade).

Participants must have cabozantinib permanently discontinued if transaminase elevations are accompanied by evidence of impaired hepatic function (bilirubin elevation >2 ×ULN), in the absence of evidence of biliary obstruction (i.e., significant elevation of alkaline phosphatase) or some other explanation of the injury (e.g., viral hepatitis, alcohol hepatitis), as the combined finding (i.e., Hy's Law cases) represents a signal of a potential for the drug to cause severe liver injury.

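### A Cycle 1 dose reduction for a cabozantinib-related adverse event is a DLT, but a permanent Cycle 1 stop for one is not listed (minor, cheap to close)

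*Combined protocol and SAP*

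**What the plan says.** The three DLT definitions (Synopsis, Sections 5.2 and 12.1) have the same four parts, all limited to Cycle 1:

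- related non-hematologic toxicity of grade 3 or 4;
- grade 4 thrombocytopenia or neutropenia (the Synopsis adds conditions for neutropenia);
- a treatment delay for unresolved toxicity (more than 7 days in 5.2 and 12.1, 14 days or more in the Synopsis);
- "any dose reduction required during Cycle 1 due to a cabozantinib-related adverse event".

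Section 5.2 says that the last part includes reductions for intolerable related grade 2 non-hematologic toxicity. No part mentions permanent discontinuation or grade 5.

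Section 6.0 describes what a reduction is: "reductions will be at one-dose-level increments". Section 5.4 lists reasons for ending treatment, including "Other unacceptable adverse event(s" and, at the bottom of the dose ladder, "Participants who cannot tolerate the lowest Dose Level dose for the specified study Stratum will have study treatment discontinued".

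Under 5.2 and 12.1, a participant without a DLT is evaluable after at least 80% of the planned dose and a full cycle of follow-up. Below 80% without a DLT, the participant may be replaced at the study team's discretion. Section 5.5 adds: "Participants will be followed for 30 days after removal from study or until death, whichever occurs first".

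**The concern.** The rule is stricter on the milder action. If a related low-grade toxicity leads to a one-level reduction in Cycle 1, it is a DLT. If the same toxicity ends treatment, nothing in the written definition makes it one, unless it also meets the grade or delay part.

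The definition feeds the primary objective. The data and safety monitoring plan in Appendix V ties escalation to the protocol's rules, so what counts as a DLT sets the maximum tolerated dose (MTD) in each stratum, with as few as six participants at the chosen dose. The uncounted event would still appear in the safety data, because Section 11.1.1 makes everyone evaluable for toxicity from the first dose. It would be missing only from the escalation count. There, one event can turn 2 of 6 (level fails) into 1 of 6 (level passes).

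**Working it through.** **1. Does any existing part catch a stop?**

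*Reduction.* Section 6.0 treats reductions as single steps down the dose table. A stop is not such a step.

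*Delay.* A stop is not literally a delay. Suppose it is read as one. With daily dosing in a 28-day cycle, a last dose on Day k leaves 28 − k undosed days.

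| Last dose | Undosed days | Share of dose | Status under 5.2 if no other part applies |
|---|---|---|---|
| Day 20 | 8 | 71.4% | DLT, if toxicity stays unresolved |
| Day 21 | 7 | 75.0% | not a DLT, replaceable |
| Day 22 | 6 | 78.6% | not a DLT, replaceable |
| Day 23 | 5 | 82.1% | evaluable, DLT-free |
| Day 27 | 1 | 96.4% | evaluable, DLT-free |

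The dividing line is 0.80 × 28 = 22.4, so 23 doses. Full-cycle follow-up is met after a late stop because 5.5 adds 30 days. In Stratum A Level −1 (every other day, 14 doses), the uncaught stops are a last dose on Day 21 (11/14 = 78.6%, replaceable) and on Day 23 or 25 (85.7% or 92.9%, DLT-free). At any time in the cycle, toxicity that resolves within 7 days of the stop also escapes.

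**2. Which stops can fall outside the grade criteria?**

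- *A related event below grade 3 judged unacceptable under 5.4.* The documents give no example.
- *Stops that Section 6 directs without a grade.* In 6.1.2, "Participants must have cabozantinib permanently discontinued if transaminase elevations are accompanied by evidence of impaired hepatic function" applies once bilirubin exceeds 2 × ULN. The same section's row for "at least one of AST or ALT is Grade 3" puts that grade above 5.0 × ULN, so the transaminase component can be below grade 3. No bilirubin cut-off is given.
- *Intolerance at the lowest level.* This matters for escalation only in a cohort enrolled at Level −1 (Stratum A) or Level −2 (B, C).
- *Other grade 4 hematologic toxicity.* Table 6-2 generally calls for permanent discontinuation, anemia excepted, but the DLT list names only thrombocytopenia and neutropenia.

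**3. How much could it matter?**

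The plan states no operating characteristics to reproduce. A level passes with 0 of 3, or 1 of 3 followed by 0 of 3:

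P(p) = (1 − p)³ + 3p(1 − p)⁵

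P(0.25) = 0.4219 + 0.1780 = 0.600 and P(0.33) = 0.3008 + 0.1337 = 0.434.

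Let e be the share of all participants with an uncounted stop, contained in the true rate p. If they are replaced, the effective rate is (p − e)/(1 − e); if kept as DLT-free, it is p − e. Both p and e are assumptions.

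| True rate p | e | P if counted | P if replaced | P if kept |
|---|---|---|---|---|
| 0.25 | 0.25% | 0.600 | 0.604 | 0.605 |
| 0.25 | 0.5% | 0.600 | 0.608 | 0.611 |
| 0.25 | 1% | 0.600 | 0.616 | 0.622 |
| 0.33 | 0.25% | 0.434 | 0.438 | 0.439 |
| 0.33 | 0.5% | 0.434 | 0.441 | 0.444 |
| 0.33 | 1% | 0.434 | 0.448 | 0.454 |

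The increase runs from 0.3 points (p = 0.33, e = 0.25%, replaced) to 2.2 points (p = 0.25, e = 1%, kept). A simulation of 400,000 runs at p = 0.33 gave 0.440 and 0.448 (replaced) and 0.444 and 0.454 (kept) for e = 0.5% and 1%.

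The chance of at least one such event among 16 to 42 participants is 1 − (1 − e)ⁿ: 4% to 10% at 0.25%, 8% to 19% at 0.5%, and 15% to 34% at 1%.

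**The case against.** The case for leaving the text alone is that the gap is narrow and the team would handle it sensibly. Most of the supporting points are fair.

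- For intolerable related grade 2 toxicity, Table 6-1 prescribes interruption or reduction, not a permanent stop. Every such reduction is already a DLT, and so is a long interruption for unresolved toxicity.
- A reader might infer that stops for fistula, perforation or hemoptysis go uncounted. The documents do not support that. They give no grade cut-offs for these events, and the fistulas graded in the account of Study XL184-301 (Section 2.4) were grade 3 or 5. Many such events would count by grade.
- A reader might take the Synopsis phrase "unacceptable toxicity (including DLT in cycle 1", or the separate entry in 5.4, as proof that related Cycle 1 stops were meant to lie outside the DLT count. Both lists cover the whole treatment period, so later-cycle stops need their own entry. They prove little about Cycle 1.
- A reader might infer that a treatment-related death would be left out. The text names only grades 3 and 4, but Appendix V has the Protocol Chair, Medical Monitor and Group Statistician decide whether the criteria are met. They would almost certainly call such a death a DLT.
- Under the Synopsis limit of 14 days or more, the uncaught window widens to last doses on Days 15 to 27. That comes from the mismatch with 5.2, a separate defect.

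What stands is the asymmetry itself. Section 5.2 deliberately counts some toxicity below grade 3 when the dose is reduced, and nothing in 5.4, 5.5 or 6.0 extends this to a stop.

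**Conclusion.** The point holds as a minor, inexpensive improvement. As written, a related Cycle 1 toxicity stop that misses the grade criteria and the delay rule is either replaceable or counted as DLT-free, whereas a reduction for the same event is a DLT.

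The average effect is small: 0.3 to 2.2 points on the chance that a level passes. This rests on an assumed event rate of about 1% or less and assumed true DLT rates of 25% and 33%. The documents supply neither. A reader might infer a serious bias in the MTD. Assumed rates of 5% to 15% would give increases of roughly 7 to 31 points, but nothing in the documents supports rates that high for events that must be related, treatment-ending, in Cycle 1 and outside every existing DLT part. The missing grade 5 is a wording omission, not evidence that deaths would be ignored.

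**What to change.** In Section 5.2, Section 12.1 and the Synopsis:

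1. In the dose-reduction clause, after the words for dose reduction, insert *or permanent discontinuation of cabozantinib*. The clause then makes either action a DLT when a related adverse event requires it in Cycle 1. Keep its present scope, which covers hematologic and non-hematologic events alike; limiting the addition to non-hematologic stops would create a new unevenness.
2. Change the non-hematologic grade criterion from grades 3 and 4 to grade 3 or higher.

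Such participants then have a DLT, so they are evaluable and not replaceable. The Section 6 management rules and the Cycle 1 window do not change. The delay limit could be harmonized across the three places in the same amendment.

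The cost is one sentence amended in three places. Slightly more events will count, including some lower-grade stops that the investigator chooses, so a stratum may occasionally stop one level earlier. That errs toward safety.
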